Data will be represented as frequency distributions and percentages. Values of continuous variables will be expressed as mean \pm standard deviation and median with interquartile range, as necessary. Continuous variables will be compared using independent samples t-tests or Wilcoxon rank-sum tests, where appropriate. Categorical variables will be compared by means of χ^2 tests or Fischer's exact test, where appropriate. Hemodynamic variables between ON-pump and OFF-pump procedures will be compared with Kruskal-Wallis tests. To analyze changes in echocardiographic and hemodynamic parameters and laboratory values, McNemar matched-pairs tests will be used to compare preoperative values to postoperative values after matching individual patient data. For all analyses, a $p < 0.05$ will be considered statistically significant. Kaplan-Meier analysis will be used to calculate survival along with a log-rank p value when comparing ON-pump and OFF-pump groups. Actuarial survival at 30-days, 6-months and 1-year post-implantation will be calculated by constructing life tables. All data will be analyzed using STATA 15 software (STATA, 2017, College Station, TX).

EXPECTED RESULTS AND IMPORTANCE OF THE STUDY

As LVADs become a more widely used and accepted treatment option for patients with refractory, end-stage heart failure, it will be necessary to further optimize outcomes and reduce the incidence of postoperative complications. We believe that using off-pump LVAD implantation will significantly reduce transfusion requirements, right ventricular dysfunction and alloantibody formation. We expect that in the off-pump group, there will be less exposure to blood products, which will lead to reduced immunosenzitization. If this research finds that off-pump use can decrease the morbidity and mortality in this patient population, it will greatly influence the manner in which these patients are managed. This would reduce hospitalizations and delays in subsequent transplant planning. This would not only be of great benefit to the patient but would significantly decrease health-care costs.

RISK AND BENEFITS

As this study used two approved methods, it is a comparative effectiveness model. The risk to the patient is no more than that of any patient undergoing LVAD implantation. As the decision for eligibility for an off-pump is made based upon data and clinical evaluation, the risk of having to convert the procedure to on-pump is very small (less than 6 % of cases). The conversion is done to eliminate the risk of patients that are not able to tolerate the off-pump surgery. In our experience the off-pump insertion of the LVAD has been safe. Patients choosing to enroll in this trial are not at any additional risk as compared to that of having the procedure done outside of this trial. The benefit of participating in this trial is the contribution of novel data that is collected in a randomized fashion and will enable future cases to be decided upon quality evidence bases.

STUDY DATA COLLECTION AND STORAGE

Study data will be collected and managed using the REDCap electronic data capture tool (36). REDCap is a secure, web-based application designed to support data capture for research studies, providing: 1) an intuitive interface for validated data entry; 2) audit trails for tracking data manipulation and export procedures; 3) automated export procedures for seamless data downloads to common statistical packages; and 4) procedures for importing data from external sources.

All data will be stored on the password-protected computers. Only the principal investigator and co-investigators will have access to source documents, which will be password protected. All analysis will be completed on de-identified datasets.

DATA AND SAFETY MONITORING

The research team will follow the international, national, and institutional regulations and standards:

- Any patient that chooses to leave the study will be removed and their data up until that point will be retained in an de-identified fashion.
- Safety monitoring is accomplished through periodic review by the Primary Investigator, who will consult with the a Research Review team which will consist of a cardiac surgeon, a cardiovascular disease specialist, a biostatistician, and a pathologist. None of the Committee members will be directly involved in the study and will not work at our department.
- Further, this protocol will undergo continuing review by the Institutional Review Board at UTHealth.

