Based on our surgical team's previous experience with off-pump implantation of Jarvik 2000 (Jarvik Heart, Inc., New York, NY) in animals (22) and humans (23), we started implanting HVADs without CPB in 2011 (11). Our goal was to implant HVAD off-CPB when possible. The decision to implant an LVAD on-CPB was made intraoperatively if patient developed hemodynamic instability during positioning of the heart. We have previously showed that LVAD implantation without the use of CPB helps to minimize post-operative complications without hemodynamic compromise or excessive bleeding during implantation (6).

Left Ventricular Assist Devices and Right Ventricular Dysfunction

Outcomes after LVAD implantation are critically dependent on right ventricular (RV) function. This means that the ability of the RV to keep up with the improved blood flow following LVAD greatly effects how well a person does following surgery. It is understood that a high pulmonary artery (PA) pressure (pressure in the blood vessel that takes blood from the right side of the heart to the lungs) measured before surgery, indicates that a higher risk of right heart failure (RHF) exists after LVAD implantation. Development of RHF in LVAD patients has a direct effect on mortality and is associated with a prolonged ICU stay and hospital admission (24). RHF in LVAD patients leads to increased morbidity and is associated with worse outcomes after cardiac transplantation (25). Despite improvements in surgical and medical management the incidence of RHF after LVAD implantation has plateaued at approximately 20-30% (26). The intra-operative technique used during LVAD implantation may play a role in the preservation of RV function. Cross-clamping and cardioplegia may compromise RV contractility (27).

Left Ventricular Assist Devices and Coagulation-Fibrinolysis Changes during On-Pump and Off-Pump LVAD implantation

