Prior to surgery, all consecutive patients scheduled for LVAD implantation will be screened for inclusion into the study. If the patient fulfills the inclusion criteria for the study, he/she will be approached and the study will be described. If the patient agrees to participate, he /she will be given written, informed consent for inclusion in the study. Baseline demographic and clinical characteristics of patients, echocardiographic parameters, hemodynamic data from right heart catheterization and blood samples will be collected. These procedures are a part of standard of care procedures, so the patients will not suffer any discomfort or additional cost due to the inclusion in the study. However, patients will be asked to provide additional blood samples for advanced hemostatic assays and panel reactive antibodies. Randomization is done intraoperatively as detailed later. In cases where the patient will not be eligible for inclusion into the study prior to randomization (e.g. if during the heart positioning the patient becomes hemodynamically unstable and the CPB will a priority have to be used), the additionally collected blood samples will be discarded. The operation is initiated by a standard procedure and all postoperative management will be completed according to institution protocols and standard of care medical guidelines.

Randomization will be done with the help of the REDCap (REDCap electronic data capture tools hosted at UTHealth) (36), a software program that contains a randomization module using stratified randomization (by type of LVAD therapy).

The primary hypothesis is that off-pump LVAD surgery compared with on-pump LVAD surgery reduces a composite outcome of right ventricular dysfunction, thrombotic complications and survival in the short term (30 days) and that these benefits are maintained at long term (1 year). The secondary hypothesis is that off-pump LVAD surgery compared with on-pump LVAD surgery reduces OHP leading to lower complement activation and reduced immune allosensitization in the short term (30 days) and at long term (1 year).

Inclusion criteria

- Adult (≥ 18 years of age)
- The patient has had a diagnosis of end stage heart failure, NYHA class III or IV HF for a minimum of 90 days prior to screening.
- The patient has guideline-directed medical therapy according to ACC/AHA/ESC HF guidelines
- The patient has an Interagency Registry for Mechanically Assisted Circulatory Support (INTERMACS) score of 1-3.

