- LVAD placement is intended as a BTT or DT with either HVAD or HeartMate III LVAD.
- The patient is able to sign informed consent form and Release of Medical Information Form.
- The patient is willing and able to participate in scheduled follow-up appointments.

Exclusion criteria

Subjects will not be enrolled into this study if they meet ANY of the following criteria:

- The patient requires concomitant surgery for left ventricular or atrial appendage closure or the patient has severe aortic insufficiency, mitral stenosis, or severe tricuspid regurgitation.
- The patient has an intracardiac thrombus or other mass diagnosed by echocardiography, left ventriculogram, or other imaging.
- Planned insertion of RV support device (either temporary or permanent).
- The patient has suffered an acute cardiovascular event such as acute coronary syndrome (ST elevation myocardial infarction (STEMI) or Non-ST elevation myocardial infarction (NSTEMI), or unstable angina), or underwent any cardiac surgery or interventional cardiac or peripheral vascular procedure within 30 days prior to LVAD implantation.
- The patient has had ischemic or hemorrhagic stroke as diagnosed by CT or MRI within 90 days prior to study enrollment.
- The patient had prior heart or other organ transplantation, or surgically implanted LVAD or cardiac shunt.
- The patient will likely need an immediate heart transplant due to hemodynamic instability.
- The patient has had a known active malignancy or treatment for cancer within the past year except for localized prostate cancer, cervical carcinoma in situ, breast cancer in situ, or non-melanoma skin cancer that has been definitively treated.
- The patient has history of any malignancy where expected survival is less than two years. Past medical history of cancer is not exclusionary as long as subject has been disease-free for at least one year since the time of diagnosis and treatment.
- Patient has a severe co-morbidity (current need for hemodialysis or current GFR \leq 20 mL/minute/1.73 m² estimated by MDRD calculation; hepatic impairment defined as liver function tests (ALT, AST, alkaline phosphatase) >3 Upper Limit of Normal within 30 days prior to LVAD implantation or known objectively confirmed intrinsic liver disease (e.g., cirrhosis, chronic hepatitis B or hepatitis C virus infection)).

- The patient has a known bleeding diathesis or thrombocytopenia defined as platelet count <50,000 platelets/ μ L.

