After standard cardiac anesthesia, surgical access to the heart for LVAD implantation will be gained through a median sternotomy in all of the patients. Scavenged blood from the operative field will be collected in a cell saver and transfused back to the patient after washing for recovery of red blood cells in all patients. Intra-operative trans-thoracic ultrasound (TEE) will be used on all patients to evaluate for associated pathologies that will require surgical management at the time of LVAD implantation and thereby contraindicate an off-pump approach. All of these procedures (median sternotomy, cell saver and TEE) are standard procedures used in cardiac surgery.

The decision to implant an LVAD on-CPB or off-pump will be made intraoperatively at this point by the surgeon. The surgeon's decision is based upon their test of the hemodynamic stability of the patient by positioning maneuver of the heart. Only patients who will be hemodynamically stable during the positioning of the heart will be included in the study and will be randomized. If the surgeon declares the patient is eligible for an off-pump procedure, a prepackaged envelope will be opened that indicates whether the procedure is to proceed off-pump or if an on-pump procedure will be used. (A pre-specified envelope will be created prior to each surgery with the assistance of REDCap).

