Preparation of buffy coat: Buffy coat will be removed after the first spinning of the centrifuge and decanted into Eppendorf tubes. The remaining packed RBCs in tubes will be stored for later (storage at -80°C).

DETERMINATION OF ALLOANTIBODIES

The measurement and assessment of alloantibodies is now a standard of care test performed on patients scheduled for LVAD surgery. A single-bead antigen assay on the Luminex platform (One Lambda Inc., Canoga Park, CA) is used at the institution. Mean fluorescence intensity (MFI) >4,000 is considered the threshold of clinical significance. Whenever the alloantibodies and panel reactive antibody status (PRAs) are measured, the data will be transferred from the medical record to the case report forms.

Calculated PRA (cPRA) values will be obtained using the United Network of Organ Sharing cPRA calculator. Sensitization will be defined as cPRA >10%. LVAD-associated sensitization will be defined as cPRA >10% documented after LVAD implantation in patients with cPRA <10% before LVAD implantation.

STATISTICAL METHODS

We calculated a sample size of 140 patients (70 in each arm), which will provide 80% power to detect a 30% relative risk reduction for the composite primary outcome at 30 days. The intention-to-treat principle, in which all participants will be included in their assigned treatment groups regardless of actual surgical procedure performed, will guide all analyses.

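### Randomisation is stratified by type of LVAD therapy but the planned chi-square, Fisher and log-rank tests ignore the stratum: valid, but a stratified analysis is a cheap, minor improvement

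*Combined protocol and SAP*

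**What the plan says.** Under Study Design and Patients, allocation uses REDCap, "a software program that contains a randomization module using stratified randomization (by type of LVAD therapy". The levels of that factor are not given. The inclusion criteria allow two readings, treatment intent or device: "LVAD placement is intended as a BTT or DT with either HVAD or HeartMate III LVAD".

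The Surgical Technique section adds that "A pre-specified envelope will be created prior to each surgery with the assistance of REDCap", but also that "Only patients who will be hemodynamically stable during the positioning of the heart will be included in the study and will be randomized". No block size is stated, and nothing says whether an assignment prepared for a patient who is not randomised is used again.

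Statistical Methods is the only analysis text. It names no test for the primary composite. As a binary outcome, the composite falls under the general rule: "Categorical variables will be compared by means of χ^2 tests", or Fisher's exact test. For survival, "Kaplan-Meier analysis will be used to calculate survival along with a log-rank p value when comparing ON-pump and OFF-pump groups". No stratified test, covariate or regression model is planned for any outcome, and the stratification factor is not mentioned again. The sample size is 70 per arm, "which will provide 80% power to detect a 30% relative risk reduction for the composite primary outcome at 30 days".

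**The concern.** The usual practice is to analyse by the factors used to randomise. If the stratum predicts the outcome and the arms are balanced within strata, the true variance of the treatment difference is smaller than an unstratified test assumes. That test then rejects too rarely under the null and gives up some power. If allocation is not balanced within strata, the unstratified test keeps its nominal level, but it leaves chance imbalance in a prognostic factor uncorrected, and this also costs power. At stake is a modest amount of precision on the primary endpoint, in a trial whose statement of 80% power comes with no control rate from which spare power could be judged.

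**Working it through.** **Inputs from the protocol.** 140 patients, 1:1, 30% relative reduction (risk ratio 0.70), significance at p < 0.05 (sidedness not stated; two-sided assumed).

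**Assumptions.** No control rate for the composite and no rate by stratum is given. Three mean control rates are used:
- 25%, as an illustration: the Background says "the incidence of RHF after LVAD implantation has plateaued at approximately 20-30" per cent, and this is the midpoint.
- 40%, as an intermediate value.
- 75%, for the reason in step 1.

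The gap between the two strata's control rates is varied from 0 to 40 points around each mean (0 to 30 at 25%). Allocation is either blocked (exactly balanced within strata) or unblocked (simple 1:1), because the documents settle neither.

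**1. The plan's own figure.** For n = 70 per arm, power = Φ{[(p1 − p2) − 1.96·√(2p̄(1−p̄)/n)] / √([p1(1−p1) + p2(1−p2)]/n)}. With p1 = 0.752 and p2 = 0.7 × 0.752 = 0.526, the difference is 0.2255, p̄ = 0.639 and the two standard errors are 0.0812 and 0.0789. This gives Φ[(0.2255 − 0.1591)/0.0789] = Φ(0.84) = 80%. The stated power therefore corresponds to a control rate near 75%. Exact enumeration at 75% gives 79.8%. The stated sample size can be neither confirmed nor refuted without the planned rate.

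**2. The two tests.** The unstratified test is the Pearson chi-square on the pooled 2×2 table. In stratum k, with n1k and n0k patients per arm, Nk in total and tk events, CMH uses the observed-minus-expected events dk and Vk = n1k·n0k·tk·(Nk − tk)/[Nk²(Nk − 1)]. The statistic is (Σdk)²/ΣVk, without continuity correction.

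**3. Power for the composite.** Change in percentage points, CMH minus chi-square; 400,000 simulated trials per cell.

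| Mean control rate, strata, allocation | gap 0 | 10 | 20 | 30 | 40 |
|---|---|---|---|---|---|
| 25%, equal, blocked | -0.3 | 0.0 | +0.8 | +2.4 | – |
| 25%, equal, unblocked | -0.3 | -0.1 | +0.4 | +1.2 | – |
| 40%, equal, blocked | -0.4 | 0.0 | +1.2 | +2.8 | +4.9 |
| 40%, equal, unblocked | -0.5 | -0.3 | +0.4 | +1.6 | +3.5 |
| 40%, 80/20, blocked | -0.6 | -0.3 | +0.5 | +1.6 | +3.0 |
| 40%, 80/20, unblocked | -0.6 | -0.4 | -0.1 | +0.6 | +1.6 |
| 75%, equal, blocked | -0.3 | +0.1 | +1.1 | +2.5 | +4.0 |
| 75%, equal, unblocked | -0.6 | -0.2 | +0.8 | +2.6 | +5.2 |

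As an example of the levels behind these differences, at mean 40%, gap 40, blocked, power is 31.2% for chi-square and 36.0% for CMH.

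**4. Type I error (equal strata).** Unblocked chi-square: 5.0-5.1% at every gap. Blocked chi-square: 4.4-5.1% at gaps up to 20, 3.8% at 30 and 2.8-3.1% at 40. CMH: 4.8-5.1% throughout.

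The blocked figure at gap 40 can be checked by hand for stratum rates of 20% and 60%. The true variance is proportional to the mean of 0.2 × 0.8 and 0.6 × 0.4, which is 0.20. The test assumes 0.4 × 0.6 = 0.24. The effective critical value is 1.96/√(0.20/0.24) = 2.15, so the two-sided rejection rate is about 3.2%, against 3.1% simulated.

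**5. Survival.** Assumed mean 1-year control mortality 20%, hazard ratio 0.5, 100,000 runs. Stratified minus unstratified log-rank power at gaps 0/10/20/30: blocked 0.0, +0.5, +1.8, +4.4; unblocked -0.2, +0.1, +1.3, +3.0.

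**6. More than two strata.** If intent and device are crossed (four strata), the factor is not prognostic, allocation is unblocked and the control rate is 40%, power goes from 32.5% to 31.6%, a cost of about 0.9 of a point.

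**The case against.** The strongest reply is that nothing here is an error. Stratifying for balance and then using a marginal test is coherent, and the test keeps its level. That stands: the protocol does not contradict itself.

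Second, no passage says that treatment intent or device predicts the 30-day composite, and gains well above 1 point on it need gaps of 30-40 points between strata. At gaps of 0-10 points the stratified test is level or marginally worse. That stands too, and it is why the point ranks low.

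Third, other choices matter more. The unstated control rate moves power from about 19% at 25% to 80% at 75%. Choosing Fisher instead of chi-square costs 5 to 7 points (17.4% against 23.4% at a 30% control rate, 36.8% against 43.7% at 50%, 75.0% against 80.0% at about 75%). This is correct and puts the present point in proportion. It does not remove the reason to name one test for the primary outcome.

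Fourth, survival beyond 30 days is listed only among the other outcome measures, so the log-rank change has limited value. That is accepted.

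In the other direction, a reader might infer that ignoring the stratum inflates false positives or makes the planned test invalid. The calculations show the opposite: the error rate is nominal or below it. Nor can one assert that power will be lost, because that needs a prognostic stratum, which the documents do not establish.

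**Conclusion.** The mismatch is real and minor. The planned tests are valid, and a positive result from them stands. For the composite, with two strata, a stratified test changes power by about -0.6 to +0.1 points at stratum gaps of 0-10 points, -0.1 to +1.2 at 20, and +0.6 to +5 at 30-40. The stratified log-rank gains up to about 1.8 points at a gap of 20 and 3.0-4.4 at 30. The unstratified chi-square becomes clearly conservative, rejecting in about 3% of trials under the null, only if allocation is balanced within strata and the gap is about 40 points. A reader might take that case as the expected one. The documents do not support this, because they state no blocking and leave the reuse of prepared envelopes open.

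The sizes rest on assumed gaps, stratum shares and control rates, a two-sided 5% level, and the same risk ratio in both strata. The case for change is that little is lost if the stratum is not prognostic and somewhat more is gained if it is strongly so.

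**What to change.** 1. Name in Statistical Methods the levels of the stratum actually used to randomise: BTT/DT, HVAD/HeartMate III, or both crossed. No stratified test can be specified until this is done.
2. Make the primary test of the 30-day composite a CMH test without continuity correction, stratified by that factor. Report a Mantel-Haenszel risk ratio with its 95% CI, which matches the relative risk reduction used for the sample size.
3. Use a stratified log-rank test for survival.
4. Keep the unstratified chi-square and log-rank tests as sensitivity analyses. The tests for continuous outcomes can stay as planned.

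The cost is two or three sentences, with no new data (the stratum is already needed to randomise) and no change to the sample size. The downside, if the stratum turns out not to be prognostic, is about 0.3-0.6 of a power point for the composite with two strata and about 0.9 with four.

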Patients undergoing implantation of CF-LVADs have a higher incidence of thrombotic and bleeding complications. Previous investigators found higher leukocyte counts, more neutrophil activation (28), and increased cytokine activation (29) in on-pump surgeries compared with off-pump cardiac surgeries. Recently, it was also demonstrated that the complement system is less activated by off-pump surgery (30). CPB activates platelets and coagulation factors, which causes impairment of hemostasis (31). The exact extent of hemostatic and fibrinolytic derangements in off-pump versus on-pump LVAD implantation is unknown.

Overall hemostasis potential (OHP) in plasma is a global functional test for assessing hemostatic potential and predicting clinical outcomes (bleeding, thrombosis). OHP in plasma is a newly developed laboratory method based on spectrophotometric measurement of the area under the curve for fibrin activation in citrated plasma samples (32). It is potentially useful for a rapid, and simple, bedside evaluation of patients with hemostatic dysfunction.

Other techniques for similar determinations, such as thromboelastography, require special equipment. With thromboelastography, the measurements should be performed on whole-blood samples within eight hours after sampling, and frozen samples cannot be used. Moreover, the observation time is up to several hours if the whole hemostatic process, especially the fibrinolysis part, is monitored. In contrast,

a global hemostatic assay for determination of overall hemostatic potential in plasma is inexpensive and relatively rapid. Estimation of OHP, coagulation, and fibrinolysis potential is finished in 40 minutes. With the exception of a common kinetic microplate reader, no special equipment is necessary for a global hemostatic assay. In addition, this technique is also useful for research purposes because frozen samples may be used.

There has not been a randomized study that has compared OHP in patients undergoing on-pump versus off-pump LVAD implantation. We speculate that with measurement of the OHP, it will be possible to better monitor the anticoagulant effects of antithrombotic drugs and prevent thrombotic and bleeding events. Further, by measuring the OHP, we might be able to stratify patients in different risk groups for thrombotic and bleeding complications.

Immunologic effects of LVAD after On-Pump versus Off-Pump LVAD implantation

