the blood contacting surfaces of device inflow cannula or outflow conduit or grafts. This will be reported via direct visual inspection (documented by a photograph if available) on pump removal or by sending the pump back to manufacturer for evaluation. Any pump explanted for suspected device thrombosis will be sent back to manufacturer for analysis. All pump thrombosis events will be adjudicated by an independent committee, the Research Review Committee which is described below in the Data and Safety Monitoring Section.

- For patients who will **die in the hospital within 30 days**, the cause of death will be confirmed by postmortem examination performed by a pathologist who will be unaware of the study assignments.

Secondary Outcome Measures

1. Need for blood product transfusion within 48-hours post LVAD implantation
2. Operative safety outcomes: incidence of 30-day mortality (from the day of surgery to 30 days [+/- 3 days]), chest tube output in the first post-operative 24 hours, rate of post-operative re-exploration for bleeding
3. Incidence of allosensitization at 30-days, 6-months and 12-months post-LVAD implantation. Allosensitization is defined as calculated panel reactive antibody (cPRA) > 10%.
4. Readmission for heart failure (follow-up 1 year)
5. OHP, overall coagulation potential and overall fibrinolytic potential in the perioperative period
6. Major bleeding defined as an episode of suspected internal or external bleeding that results in one or more of the following: death, re-operation, hospitalization, transfusion of red blood cells according to INTERMACS definition.

Other Outcome Measures

1. Duration of surgery (skin incision to skin closure)
2. Duration of postoperative mechanical ventilation (length of time from intubation until patient is extubated)
3. Length of ICU stay (length of time from ICU admission from surgery until ICU discharge)
4. Length of hospital stay (length of time from surgery to hospital discharge)
5. Incidence of renal dysfunction defined by INTERMACS criteria
6. Incidence of 30-day mortality (from the day of surgery to 30 days [+/- 3 days])
7. Incidence of post-operative mortality within 6 months and 1 year

8. Device-related complications totaled at 30-days, 6-months and 12-months post-LVAD implantation.
9. Duration and amount of intraoperative and postoperative inhaled nitric oxide use

COLLECTION OF BASIC DATA/PATIENT CHARACTERISTICS

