To evaluate the role of CPB on hemostatic and fibrinolytic parameters, we will make sure that the perioperative level of heparinization will be comparable between groups.

All patients will be postoperatively treated with 81mg aspirin daily and coumadin with a target international normalized ratio range of 2.0–2.5. Data on the use of antithrombotic therapy will be recorded at baseline and at each follow-up appointment. Time-in-Therapeutic Range (TTR) will be calculated using the Rosendaal method as a measure of quality of anticoagulation dose management (42).

Use of tranexamic acid

Tranexamic acid is a well-documented fibrinolytic inhibitor. The medical team will be advised to use always the same dose of tranexamic acid (if the patient's condition will allow it) in the perioperative period as it has an effect on overall fibrinolytic potential.

SELECTION OF SURGEONS

All surgical procedures will be performed by an "experienced" cardiac surgeon with more than 5 years of practice in cardiac surgery after residency training and has performed more than 100 LVAD implantations. Primary surgeons have experience with both techniques (on-pump and off-pump LVAD implantation). All procedures will be done under the supervision of an "expert" cardiac surgeon ([name]/PI of this protocol) who has more than 30 years of experience in advanced and complex cases of cardiac surgery, has performed more than 500 LVAD implantations, and is very experienced with both techniques (on-pump and off-pump LVAD implantation). Residents and fellows will not be eligible to participate as primary surgeons in the trial.

BLOOD COLLECTION AND PREPARATION

For research purposes, two additional vials of blood will be collected at the same time that standard of care blood draws are done. The timepoints for the research blood draws will be at baseline (within 48 hours of surgery), within 24-48 hours post-operation (but before discharge), 30 days, 6 months and 1 year. For the follow-up blood draws (+/- 5 days is acceptable).

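### The secondary hypothesis is only partly matched by planned outcomes: complement is never measured, the causal chain is untested, and OHP is an outcome only perioperatively

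*Combined protocol and SAP*

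**What the plan says.** **Hypothesis.** Study Design and Patients states that off-pump surgery, compared with on-pump surgery, "reduces OHP leading to lower complement activation and reduced immune allosensitization". The sentence then closes with a time phrase that names 30 days as the short term and 1 year as the long term.

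**Outcomes.** Secondary Outcome Measures contains two matching items. Item 3 is "Incidence of allosensitization at 30-days, 6-months and 12-months post-LVAD implantation", with sensitization defined as a calculated panel reactive antibody value above 10%. Item 5 is "OHP, overall coagulation potential and overall fibrinolytic potential in the perioperative period".

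**Samples.** Blood Collection and Preparation schedules research draws at baseline and then "within 24-48 hours post-operation (but before discharge), 30 days, 6 months and 1 year". Study Design and Patients gives their purpose: "patients will be asked to provide additional blood samples for advanced hemostatic assays and panel reactive antibodies". The background section on coagulation and fibrinolysis says of the OHP assay that "this technique is also useful for research purposes because frozen samples may be used". It describes the assay in citrated plasma, whereas Blood Collection and Preparation names only K2 EDTA tubes for plasma.

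**Complement.** Outside the hypothesis, the one substantive mention is in the background: "it was also demonstrated that the complement system is less activated by off-pump surgery". The word also occurs in the title of a cited paper.

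**Analysis.** Statistical Methods compares continuous variables between arms by t-test or rank-sum test, and compares preoperative with postoperative laboratory values within patients. It contains no model relating OHP to complement or to sensitization.

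**The concern.** A stated hypothesis commits the trial to a conclusion. This one names three effects, puts them in causal order and gives two times. Where an effect has no outcome, the report cannot draw that conclusion however the data fall.

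Two practical risks follow. First, plasma will be in the freezer from 30 days, 6 months and 1 year. If OHP is later run on it, the choice of time point will be post hoc, because outcome 5 stops at the perioperative period. Second, an OHP difference and a sensitization difference seen together could be reported as support for the whole chain, although its middle link was never observed.

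The protocol's own reasoning elsewhere differs from the chain. The background on immunologic effects and the section on expected results both attribute lower sensitization to fewer transfusions, not to lower OHP.

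**Working it through.** The plan gives no figure to reproduce on this point, so the check sets the hypothesis beside the outcomes.

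**Step 1. Coverage, reading the times as applying to every part.**

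| Part of the hypothesis | 30 days | 1 year | Source |
|---|---|---|---|
| OHP | no outcome | no outcome | secondary outcome 5, perioperative only |
| Complement activation | not measured | not measured | absent from outcomes, laboratory list, blood processing and statistics |
| Allosensitization | outcome | outcome | secondary outcome 3, also at 6 months |

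3 parts × 2 times = 6 combinations, of which 2 have an outcome.

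**Step 2. Coverage, reading the times as applying to allosensitization only.** The sentence allows this, because the time phrase follows allosensitization directly. OHP is then an early effect of surgery and outcome 5 matches it. Allosensitization is matched as before. Complement still has no measurement at any time.

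**Step 3. The causal link.** Under either reading, testing the chain would need complement data and an analysis relating OHP to what follows. The plan has neither. The planned preoperative-to-postoperative comparison of laboratory values is within patients. It is neither a comparison of arms nor a test of the chain.

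**Step 4. Can the late OHP gap be closed with planned samples?** Five research draws are scheduled, and those at 30 days and 1 year coincide with the hypothesised times. The gap is therefore in the outcome definition, not the sampling schedule. With 140 patients and one assay per patient and visit, 140 × 2 = 280 further assays. This is an upper limit, since it assumes that every patient survives, attends and gives a usable sample.

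**Step 5. Is the plasma suitable?** The assay is described in citrated plasma and the only plasma tube named is K2 EDTA. The documents do not reconcile the two. This affects perioperative OHP as much as late OHP.

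**Step 6. The comparison of arms.** A baseline sample is planned within 48 hours of surgery, but the default t-test or rank-sum test on a postoperative value does not use it. An analysis with baseline OHP as covariate uses data already collected and is more precise to the extent that baseline predicts the later value. The documents give no correlation, so the gain cannot be quantified.

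**The case against.** The strongest reply is that the perioperative window looks deliberate. Under perioperative management, the protocol aims for comparable heparinization between arms and advises a uniform tranexamic acid dose because of its effect on fibrinolytic potential. After surgery all patients receive aspirin and coumadin, so late OHP would partly reflect that treatment. On this view the 30-day and 1-year times belong to allosensitization, OHP is correctly early, and the causal wording only states a rationale. This stands as a defence of outcome 5: adding late OHP is a design choice, not a necessity. It does not supply a complement measurement, and it leaves the sentence open to two readings.

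A reader might also go further than the documents allow, in three ways:

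- **That the secondary hypothesis cannot be answered at all.** Its clinical endpoint is covered at 30 days, 6 months and 12 months, and Determination of Alloantibodies gives the assay, the calculator and a definition of LVAD-associated sensitization.
- **That the three later draws serve no outcome.** They feed no OHP outcome, but the additional samples are also for panel reactive antibodies, which are needed at exactly those visits.
- **That extending OHP is free.** It needs extra assays and depends on resolving the tube question.

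**Conclusion.** The mismatch is real but limited. Complement activation is hypothesised and never measured, so no result of this trial can support that step or the chain through it. This holds under either reading of the sentence. The OHP timing is ambiguous: under the wider reading, OHP at 30 days and 1 year has no outcome; under the narrower reading, outcome 5 is adequate and only the wording needs repair. Allosensitization is properly matched.

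The point concerns a secondary hypothesis. It does not touch the primary composite, its sample size or the allosensitization comparison, and it ranks as a minor improvement. The conclusion rests on the text alone, and assumes that no separate laboratory manual defines a complement assay or late OHP outcomes.

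**What to change.** 1. **Hypothesis (Study Design and Patients).** Delete the complement step and the causal wording, and state two separate effects. For example: *Relative to on-pump implantation, off-pump implantation (a) lowers OHP at [named times] and (b) lowers the incidence of allosensitization at 30 days and at 1 year.* If the investigators want to keep complement, they need a named assay, an outcome and time points. Cost of deletion: wording only.

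2. **OHP times.** Choose one. Either state in the hypothesis that the OHP effect is perioperative and name the draws meant (baseline and 24–48 hours), or extend secondary outcome 5 to 30 days and 1 year using the plasma scheduled at those visits. If extended, state that late OHP also reflects postoperative aspirin and coumadin. The first option costs wording. The second adds up to 280 assays, which the protocol describes as inexpensive, and needs no new visits or draws. It is cheap, not free.

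3. **Analysis (Statistical Methods).** Compare OHP between arms at each named time with the baseline value as covariate. Cost: a sentence and a little analysis.

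4. **Before any stored plasma is used for OHP**, reconcile the citrated plasma of the background with the K2 EDTA tubes of Blood Collection and Preparation. This applies to the perioperative samples too.
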